6.2.2 FORMULATION, APPEARANCE, PACKAGING, AND LABELING

SYD-101 and Vehicle are clear ophthalmic solutions packaged in identical white, 5-mL low-density polyethylene (LDPE) ophthalmic bottles and supplied by Syndexis or its designee. All study drugs will

be labeled with the protocol number and medication kit numbers. The label will also specify the storage conditions (room temperature) and state that the study drug is limited to investigational use.

6.2.3 PRODUCT STORAGE AND STABILITY

The study drug must be stored between 5°C (41°F) and 25°C (77°F) and protected from excessive heat. Do not freeze. Temperature will be monitored while stored at sites. Refer to the Pharmacy Manual for further information.

6.2.4 PREPARATION

Not applicable.

6.3 MEASURES TO MINIMIZE BIAS: RANDOMIZATION AND MASKING

Allocation to study treatment will occur in a double-masked manner on 2 occasions: **initial randomization** at Baseline (for Primary Treatment Period [Part 1]) and **re-randomization** at Month 36 (for Randomized Withdrawal Period [Part 2]).

For Part 1, prior to initiation of study treatment, randomization will occur by site staff via the IVRS/IWRS once it is confirmed that the participant meets the final study entry criteria (see [Sections 5.1](#) and [5.2](#)). The IVRS/IWRS will provide the participant identification number used on all study documents and will be used to manage the randomization and treatment assignment based on a stratified randomization scheme prepared by Sydnexis' designee. Initial randomization will be in a 1:1:1 ratio of SYD-101 0.01%: SYD-101 0.03%: Vehicle and stratified by baseline SE (0.50 D to 3.0 D and >3.0 D to 6.0 D) and age (3 years to <6 years, 6 years to <9 years, 9 years to <12 years, and 12 years to 14 years).

To maintain treatment masking for Part 2, sites will contact the IVRS/IWRS at Month 36 for all participants. At Month 36, participants who were initially assigned (at Baseline) to SYD-101 0.01% will be re-randomized in a 1:1 ratio to masked SYD-101 0.01% or Vehicle; participants initially assigned (at Baseline) to SYD-101 0.03% will be re-randomized in a 1:1 ratio to masked SYD-101 0.03% or Vehicle. The Re-randomization of SYD-101 participants will not be stratified. All participants who were initially assigned (at Baseline) to Vehicle will be re-randomized to masked SYD-101 0.03% at Month 36.

Sites will also contact the IVRS/IWRS at the time a participant qualifies to initiate treatment with escape medication (ie, at confirmatory visit when measurements confirm progression of myopia ≥ 2.00 D in SE from baseline) for ANY participant who has qualified for and desires to use escape medication.

Study drug will be labeled with medication kit numbers, and the IVRS/IWRS will provide each site with the specific medication kit number(s) for each randomized participant at the time of

randomization and any required drug resupply visit. Additionally, to maintain study masking, the IVRS/IWRS will assign a new medication kit for all participants at any timepoints study treatments might switch based on study design (ie, the re-randomization at Month 36, at escape for confirmed ≥ 2.00 D progression), even if the new medication kit will be of the same treatment type of the medication kit currently assigned. Sites will dispense study drug according to the IVRS/IWRS instructions. Sites will receive the IVRS/IWRS confirmation notifications for each transaction. All notifications are to be maintained with the study source documents.

Masking of individual participant treatment assignments will be maintained throughout the study for all participants and required site staff until the database is locked for the EOS analysis at Month 48. If it is necessary for the safety and appropriate treatment of a participant, the treatment assignment can be unmasked by the site via the IVRS/IWRS. When possible, the medical monitor should be notified prior to the unmasking, and the reason for breaking the mask will be documented in the source documentation. The investigator should inform the medical monitor of the unmasking if there is no notification prior to the unmasking. The treatment assignment for the participant can be determined by designated site staff calling into the IVRS/IWRS via password-protected access. The reason for breaking the code must be recorded in the participant's source documents and electronic case report form (eCRF).

To minimize bias, results of the Month 24 analyses for EU submission will neither be made public, nor shared with study sites nor study monitors until after completion of the Month 36 analysis.

6.4 STUDY INTERVENTION COMPLIANCE

Participants will be queried on adherence to the dosing regimen on the Activities/Compliance Questionnaire. Refer to the MOP for further information.

6.5 CONCOMITANT THERAPY

The decision to administer a prohibited medication/treatment is done with the safety of the study participant as the primary consideration. Whenever possible, the medical monitor should be notified before the prohibited medication/treatment is administered.

Medication considered necessary for the participant's welfare may be given at the discretion of the investigator. Participants should be instructed to maintain a stable dose of chronic medications during the study whenever possible. All concurrent medications (prescription, over-the-counter, and supplements), adjunct therapies, and concurrent procedures will be recorded on the appropriate eCRF page.

Topical drops for examination procedures, such as anesthetics, dilating agents, and fluorescein are permitted. Acute use of eye drops for allergies or anti-infective eye drops for treatment of bacterial or viral conjunctivitis is permitted; however, administration of any such treatment must precede that of the study drug by 15 minutes.

1% Cyclopentolate will be used for cycloplegic autorefraction measurements in this study.

6.5.1 PROHIBITED THERAPY

Due to the potential for drug-drug interactions, monoamine oxidase inhibitors are prohibited. Refer to the MOP for further information.

During the study, participants must not use the following:

- Any lenses to reduce myopia progression is prohibited, including but not limited to orthokeratology, rigid gas-permeable, bifocal, progressive-addition, and multi-focal lenses
- Any anti-muscarinic agent for myopia, including but not limited to atropine and pirenzepine

6.5.2 ESCAPE MEDICATION

For participants with measured myopia progression ≥ 2.00 D from baseline in SE at a visit occurring between Month 18 and Month 36 (inclusive), and myopia progression is confirmed 6 months later at the next scheduled visit (ie, visit between Month 24 and Month 42 [inclusive]), treatment with **escape medication** (active SYD-101 0.03% on an open-labeled basis) may be initiated at the confirmatory visit and continued until Month 48.

As with masked study treatment, open-label SYD-101 0.03% (escape medication) will be provided by the sponsor, managed and tracked using IVRS/IWRS, and dispensed to participants by the study coordinator.

7 STUDY DRUG DISCONTINUATION AND PARTICIPANT DISCONTINUATION OR WITHDRAWAL FROM STUDY

7.1 DISCONTINUATION OF STUDY DRUG

Discontinuation from study drug does not mean discontinuation from the study, and remaining study procedures should be completed as indicated by the study protocol. If a clinically significant finding is identified (including, but not limited to changes from baseline) after enrollment, the investigator or qualified designee will determine if any change in participant management is needed. Any new clinically relevant finding will be reported as an AE.

The data to be collected at the time of study intervention discontinuation will include the procedures as listed in the schedule of activities.

7.2 PARTICIPANT DISCONTINUATION/WITHDRAWAL FROM THE STUDY

Participants are free to discontinue the study at any time, for any reason, and without prejudice to further treatment. The investigator may remove a participant if, in the investigator's judgment, continued participation would pose unacceptable risk to the participant or to the integrity of the study data. Reasons for removal or withdrawal might include the following:

- Withdrawal of consent
- Administrative decision by the investigator or sponsor
- Significant protocol deviation
- Participant noncompliance or other significant protocol deviation
- Pregnancy
- Safety concern by the investigator or sponsor
- Lost to follow-up

With the exception of withdrawal of consent, participant withdrawal should be discussed with the sponsor, when possible, prior to withdrawing. Notification of early participant discontinuation from the study and the reason for discontinuation will be made to Syndexis and will be clearly documented on the appropriate eCRF. If a participant discontinues prior to completing the study, the procedures outlined for the Month 48 visit should be performed at the ET visit (ie, last visit the participant attends).

Participants who sign the ICF and are randomized but do not receive study drug may be replaced by randomization of an additional participant (ie, the replacement participant will not necessarily receive the same treatment assignment as the original participant being replaced). Participants who sign the ICF, are randomized and receive the study intervention, and subsequently withdraw, or are withdrawn or discontinued from the study, will not be replaced.

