8.4 REPORTING OF PREGNANCY

If a female participant becomes pregnant during the study, the investigator will notify the sponsor's designee and the medical monitor immediately after the pregnancy is confirmed, and the participant will be permanently discontinued from study drug but remain in the study for monitoring of safety and outcome of pregnancy. The investigator will (1) notify the participant's physician that the participant was being treated with the study drug, and (2) follow the progress of the pregnancy to term on the participant providing written informed consent for release of these data. The investigator should document the outcome of the pregnancy and provide a copy of the documentation to the sponsor's designee.

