| Treatment Discontinuation | 
EMA Endpoint: Hypothetical
 
 • Observations after DC due to a related AE will be multiply imputed assuming missing not at random (MNAR) using a sequential vehicle-based pattern regression • Observations after Treatment DC for other reasons will be multiply imputed assuming MAR 
FDA Endpoint: Composite
 
 • Participants with discontinuation (DC) due to a related AE are non-responders • Observations after DC for other reasons will be multiply imputed assuming MAR | 
Discontinuation due to related AE are labelled non-responders is a conservative strategy as the discontinuation is related to treatment. Other reasons for discontinuation will be considered to occur at random
 
Treatment policy will be used as a sensitivity analysis as this will reflect real world use including potential rebound effect when participants discontinue treatment
 |
| Study Discontinuation | 
EMA Endpoint: Hypothetical
 
 • Observations after DC due to a related AE will be multiply imputed assuming MNAR using a sequential vehicle-based pattern regression • Observations after Treatment DC for other reasons will be multiply imputed assuming MAR 
FDA Endpoint: Composite
 
 • Participants with DC due to a related AE are non-responders • Observations after DC for other reasons will be multiply imputed assuming MAR | 
This study was enrolling, and a large portion of participant follow-up was during the ongoing COVID-19 pandemic. The majority of study discontinuations are logistical due to withdrawal of consent.
 
Discontinuation due to related AE are labelled non-responders and is a conservative strategy as the discontinuation is related to treatment. Other reasons for discontinuation will be considered to occur at random.
 |
| Invalid SE Values | 
Treatment Policy
 
 • Invalid SE values will be used | 
Given the age of children in participants, in clinical practice it would be expected to have non-ideal auto-refraction assessments.
 |

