9.2 SAMPLE SIZE DETERMINATION

[figure not shown]
Group sample sizes of 280 in each treatment arm will achieve at least 90% power to detect a difference in the percentage of participants with myopic progression (>0.75 D) of at least 15% between a SYD-101 arm and Vehicle. Power calculations presented in Figure 9-1 are based on the Chi-squared test at a 2-sided significance level of 0.025.

Figure 9-1: Power for 2-Sided Chi-Square Test Evaluated at Alpha=0.025 for Proportion Responders When 280 Participants Per Arm

Additionally, group sample sizes of 280 per treatment arm achieves >90% power to detect a reduction of 0.18 D or more in the annual progression rate between SYD-101 and Vehicle, assuming a common SD of 0.60 D. Power calculations presented in Figure 9-2 are based on a 2-sample t-test evaluated at the 0.025 significance level.

Figure 9-2: Power for 2-Sided T-Test Evaluated at Alpha=0.025 for Annual Progression Rate When 280 Participants Per Arm

Calculations were performed using SAS® 9.3 Software (SAS Institute, Inc, Cary, North Carolina).

This study plans to continue follow-up for all enrolled participants through Month 48, regardless of early discontinuation of study treatment or receipt of escape medication/prohibited therapy. All participants will be included in analyses based on their observed data. Because the effect size estimates have already taken into consideration the impact of no therapy/escape medication, enrollment of additional participants beyond 280 participants per treatment arm has not been planned.

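### Section 7.2 lets investigators end study follow-up for noncompliance, protocol deviation or pregnancy, which conflicts with Section 8.4 and undercuts the follow-everyone premise of Section 9.2

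*Protocol*

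**What the plan says.** Protocol Section 7.2 concerns leaving the study. The investigator may remove a child when staying in would endanger the child or the integrity of the data. The listed reasons include an administrative decision, a significant protocol deviation, "Participant noncompliance or other significant protocol deviation", and pregnancy.

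Three other protocol sections bear on the same children:

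- Section 7.1: "Discontinuation from study drug does not mean discontinuation from the study".
- Section 8.4, on pregnancy: "the participant will be permanently discontinued from study drug but remain in the study for monitoring of safety and outcome of pregnancy".
- Section 9.2: "This study plans to continue follow-up for all enrolled participants through Month 48, regardless of early discontinuation of study treatment", and likewise after escape or prohibited therapy. It adds that everyone is analysed on observed data, and on that footing plans no enrolment beyond 280 per arm.

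For the primary estimands, Table 9-2 treats exits not due to a related AE this way: "Observations after DC for other reasons will be multiply imputed assuming MAR". Section 9.4.2 runs that imputation separately within each arm.

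**The concern.** A child removed for poor adherence is one whose later refraction may well drift towards the Vehicle course. Once the child is out of the study, that course cannot be measured. The exit counts as an other-reason discontinuation, and later spherical equivalent (SE) is drawn from the child's own arm. Table 9-2 supports MAR by describing most study discontinuations as logistical, through withdrawn consent. Removal by the investigator for adherence or deviation is neither.

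At stake are a small bias towards SYD-101 in the primary analyses and the loss of outcomes that the sensitivity analyses and two tested secondary endpoints were meant to observe. The protocol itself would create this missingness, and it would depend on investigators' judgement.

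**Working it through.** **1. The plan's own power.** Inputs from Protocol 9.2: 280 per arm, two-sided 0.025, a 15-point difference, or 0.18 D/year with SD 0.60.

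- Annual rate: 0.18 / (0.60 × √(2/280)) = 3.55. Power = Φ(3.55 − 2.24) = 90.5%.
- Proportion: the lowest chi-square power for a 15-point gap is 90.7%, at 57.5% v 42.5%.

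Both stated powers reproduce, with little to spare.

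**2. Which children are affected.** This follows from Table 9-2, Protocol 9.4.2, and SAP 8.1.2 and 8.2.

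| Child removed from the study | Effect on primary analyses | What removal loses |
|---|---|---|
| Still nominally on drug, no related AE | Changes: measured SE is replaced by own-arm MAR imputation | All later data |
| Formally stopped drug for another reason (pregnancy included) | None: later SE is MAR-imputed even if the child stays | Data used as observed in Sensitivity Analyses 2 to 7, axial length and time to progression |
| Used prohibited treatment | None: non-responder (FDA) or censored (EMA) | Later data used in Sensitivity Analysis 2 (and, for Vehicle children, Analysis 5) |

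**3. Size on the FDA endpoint.** SAP 4.1 gives mean rates of 0.65 and 0.325 D/year with SD 0.55. Progression of 0.75 D over 3 years is 0.25 D/year. Assuming normal rates, and ignoring confirmation and progression at earlier visits:

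- Vehicle: 1 − Φ((0.25 − 0.65)/0.55) = 76.6%.
- SYD-101: 1 − Φ((0.25 − 0.325)/0.55) = 55.4%.
- Gap: 21.2 points.

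The documents give no removal rate. SAP 4.1 has only 7% per year for dropout and treatment discontinuation together, or 1 − 0.93³ = 19.6% by Month 36. Suppose a share r of the active arm is removed while on drug, has no benefit over all follow-up, and is imputed wholly on the arm's course. The overstatement is r × 21.2:

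- r = 2% (5.6 of 280 children): 0.42 points.
- r = 5% (14 children): 1.06 points.

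This is a ceiling. If only half of follow-up lacks benefit, the overstatement is roughly halved.

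**4. Size on the annual rate.** With f the share of follow-up without benefit, the bias is about r × f × the treatment difference. At r = 5% and f = 1, that is 0.05 × 0.18 = 0.009 D/year.

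A simulation at the SAP rates, with visit-level error SD 0.15 D (assumption) and r = 10%, shows the mechanism at Month 24:

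- No adherence after Month 6, removed at Month 6: own-arm imputation gives an active mean of 0.326 D/year, the full-benefit value. Following the children gives 0.350. The gap matches 0.10 × 0.75 × 0.325 = 0.024.
- No adherence after Month 6, removed at Month 12: imputation gives 0.338 against 0.350. Decline seen before removal carries forward.

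**5. Against the planned effects.** If such children were followed without benefit (f = 1):

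- r = 2%: 0.18 becomes 0.176 D/year (power 89.2%), and 15 becomes 14.7 points (89.5%).
- r = 5%: 0.171 D/year (87.1%) and 14.25 points (87.3%).

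Section 9.2 says its effect sizes already allow for periods without therapy, so these figures show sensitivity and do not forecast lost power.

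**The case against.** Section 7.2 is permissive and conditional, and it asks for discussion with the sponsor where possible. Section 9.2 states a plan and does not deny that withdrawals happen. Several prespecified analyses address the assumption: Sensitivity Analyses 4 and 5 impute all study discontinuations from Vehicle, Analysis 6 counts a dropout without confirmed progression as progressed, and Analysis 3 is a tipping point on imputed SYD-101 values. Progression confirmed before removal still counts. Attrition was also examined: the SAP simulation, at 7% per year and 217 per arm, reports about 97% power (FDA) and 99.96% (EMA). The EMA figure is consistent with a simple check: 217 × 0.93² = 187.7 completers gives 99.98%.

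Most of this stands, and it limits the harm. It does not remove the text conflict on pregnancy. It also does not give back data that the schedule would have collected: Analyses 3 to 6 substitute assumptions for outcomes that could have been measured, while Analysis 2 (for non-AE exits) and Analysis 7 stay under MAR.

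A reader might go further and infer that every removed child is imputed with full drug benefit. The table in the working shows otherwise for two of the three groups, and for the third the benefit applies only to increments after removal. A reader might also infer that 7.1 is contradicted. It is not: it says only that stopping drug is not leaving the study, and 7.2 concerns leaving for other reasons.

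**Conclusion.** The inconsistency is real and should be corrected. It is direct between 7.2 and 8.4 on pregnancy. Elsewhere 7.2 permits removals that undercut the follow-up premise on which 9.2 rests its sample size. SAP 5.2 lists dosing-adherence deviations and prohibited treatment as possible major deviations, so children whom 9.2 means to follow fall within the 7.2 reasons.

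The effect on the primary results is probably small: at most about 0.4 to 1.1 points on the FDA endpoint for an assumed 2% to 5% removed on drug with no benefit throughout, and less with later removal. It could be larger only if such removals were common, and the documents give no rate. The surer cost is lost post-discontinuation data for the sensitivity analyses, axial length and time to progression. The claim that the two sets of rules can never both be followed is not supported outside pregnancy, because 7.2 is discretionary.

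**What to change.** - In Section 7.2, remove protocol deviation and noncompliance as reasons for leaving the study. State that neither the data-integrity clause nor an administrative decision may be used to end follow-up on those grounds; otherwise the same removals remain possible by another route.
- State that these children, including users of prohibited treatment, keep the scheduled autorefraction and safety visits to Month 48 unless consent or assent is withdrawn or contact is lost. Deviations are then handled through the per-protocol set, as SAP 4.3.4 and 5.2 already allow.
- Reconcile Sections 7.2 and 8.4 on pregnancy. No clinical rule is proposed here.
- For any children already removed, tabulate removals by arm and reason. Section 7.2 puts the reason on the eCRF, but the disposition summary in SAP 5.1 does not list reasons. Impute these children from Vehicle in a named sensitivity analysis.

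The cost is protocol wording, a letter to sites, one table and one sensitivity analysis. No new visits are needed. A few more off-drug children stay in follow-up, and the estimated effect may be slightly smaller.

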7.3 LOST TO FOLLOW-UP

At any point during the trial, if a participant fails to return for a scheduled visit and is unable to be contacted by the site staff, he or she will be considered lost to follow-up. This does not include a single missed visit of which the site was notified or a missed visit with subsequent contact from the participants indicating an intention to continue on the study. The following actions must be taken if a participant fails to return to the clinic for a required study visit:

- The site will attempt to contact the participant and reschedule the missed visit within the visit window and counsel the participant on the importance of maintaining the assigned visit schedule and ascertain if the participant wishes to and/or should continue in the study. If this make-up visit is outside the allowable window, a protocol deviation will be recorded.
- Before a participant is deemed lost to follow-up, the investigator or designee will make every effort to regain contact with the participant (where possible, 3 telephone calls and, if necessary, a certified letter to the participant's last known mailing address or local equivalent methods). These contact attempts should be documented in the participant's medical record or study file.
- Should the participant continue to be unreachable, he or she will be considered to have withdrawn from the study with a primary reason of lost to follow-up, and a protocol deviation will be recorded.

